- c. **To identify key factors (alcohol and drug use, social support, psychological distress, quality of life) that predict re-arrest and nights spent homeless using traditional and smart phone-based assessment approaches.** It is hypothesized that key variables that are measured in- person (e.g., alcohol/drug use, perceived social support, psychological distress, quality of life) and via daily phone-based assessments (e.g., affect, stress, discrimination, alcohol/drug use) will have direct effects on re-arrest and number of homeless nights. These key variables are also hypothesized to mediate the relation between treatment condition and number of homeless nights and re-arrest.

Study Design:

This study is a 3-arm randomized controlled trial. Specifically, male and female homeless adults who enroll in a shelter based homeless recovery program following release from either the Dallas County Jail or the Dallas City Jail (N=462) will be randomized to one of three conditions: Usual Case Management (UCM); Usual Care plus Smartphone (UCM+SP); or Usual Care plus Smartphone based Case Management (SPCM). SPCM will be delivered through a modified version of the PI's previously developed smartphone application (i.e., "app") on a study provided smartphone. The app will not provide case management and crisis intervention services directly; rather, it will prompt twice weekly contact with their case manager and provide links to service providers through the touch of a button. Primary study outcomes are service utilization, number of homeless nights, and re-arrest. Another key focus of this study is to address gaps in our understanding of the factors that drive re-arrest and homelessness by using traditional in-person (i.e., baseline, 1, 3, and 6 months post- baseline) and smartphone based (i.e., daily for 6 months) assessment methods to identify distal and proximal predictors of continued homelessness and arrest. Arrest records will be examined to determine if participants are re-arrested within 12 months of study enrollment.

Participants who are randomly assigned to the UCM+SP or SPCM conditions will receive a smartphone at the randomization visit and they will be asked to carry it with them at all times for 6 months (26 weeks). Date, time, location, and duration of SPCM app feature use (e.g., case manager calls) will be recorded by the app for future analysis. See Table 1 for a summary of study conditions.

Study Conditions

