and education. The Tukey-Kramer adjustment will be used to examine all pairwise comparisons across conditions. We will also determine if the intervention has similar effects across races, gender, and age**Aim 2**. Based on the available data in criminal justice and homeless populations, we expect a 30% reduction in alcohol and drug use days in SPCM and a 15% reduction in alcohol and drug use days in UCM+SP compared with UCM.^{3,126} Given these expected differences, the proposed sample size of 462 participants (144 per condition) will yield 90% minimum power for comparing the frequency of alcohol and drug use days across conditions. Furthermore, the proposed sample size of 462 participants has 80% minimum power to detect a 24% greater decrease in psychiatric symptoms¹²⁷ in the SPCM group and 10% greater decrease in the UCM+SP group relative to UCM.

Analyses. Multi-level models, also known as mixed models will assess the impact of condition on alcohol and drug use and psychological distress. This method considers the auto correlated nature of this data, and 'unstructured' covariance may be specified to account for the unequal spacing of observations (in-person and EMA data). Covariates for analyses will include baseline characteristics that are known predictors of each outcome, including age, race/ethnicity, employment status, criminal history, and periods of lifetime homelessness. We will also test for interactions between treatment and key demographic variables (e.g., race, ethnicity, gender, and age).

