Aim 3. The detectable effects for analyses based on a complete EMA sample size of 201 participants (allowing for 30% study drop-out; see [name] and Rosenheck³ for follow-up rates in a sample of homeless adults with both serious mental illness and substance abuse), 2-sided tests, alpha=.05, and power=.80 are presented in Table 8. Where appropriate, these estimates account for the fact that repeated observations from the same person will be correlated. The most conservative detectable effects for the GLMM EMA analyses will be presented. Thus, calculations are based on an N of 201 individuals completing 80% of 183 assessments during the 6-month EMA study period for a total of 29,426 EMAs across all participants. Since few EMA studies have been conducted in this population, we computed detectable effects using a reasonable range of intraclass correlation coefficient (ICC) values. Detectable effects estimates depend on the variance inflation factor (VIF)¹³⁴ which is based on both the size of the ICC and the average number of observations per person. The VIFs used to calculate the effective sample size are displayed in Table 8. Thus, using the EMA data, we will be able to detect factors that predict reductions in homeless nights by as little as 3.1 percentage points.

Analyses. Logistic Regression of traditional in-person assessments (e.g., substance use, social support, psychological functioning, quality of life; see Table 7 for other key constructs) and summarized EMA data (e.g., affect, stress, discrimination, alcohol and drug use) will be conducted to identify significant demographic, psychosocial, environmental, and behavioral predictors of re-arrest in the 12 months following the randomization visit (binary outcome). Covariates may include treatment group, age, gender, race/ethnicity, education, type of crime, and other variables as appropriate. Change scores (e.g., change in social support from baseline to the 1-month follow-up visit) will also be examined as potential predictors of re-arrest.

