Generalized Linear Mixed Model Regression Analyses (GLMM) will be used to examine the longitudinal effect of key risk and protective factors on number of homeless nights (measured repeatedly using a timeline follow-back procedure at in-person follow-up visits). GLMM can handle fixed and random effect model parameters, nested designs, and repeated measures with various correlation structures.^{128,129} GLMM can also handle different variance functions, unbalanced designs where the number of repeated observations varies across individuals, and the situation where assessments within a week are more highly correlated than assessments separated by multiple weeks or months. We will assess the best way to model the correlation of the repeated measures using the methods of Wolfinger¹³⁰ and statistics such as Akaike's and Schwarz's information criteria. Adjustments for multiple comparisons will be made according to Westfall and Young.¹³¹

GLMM will also be used to identify proximal predictors of homeless nights (assessed each day) using EMA data. EMAs generate an enormous amount of data; therefore, we will be able to address multiple within

and between subject questions. For example, we will examine key EMA variables (e.g., negative affect, stress) and parameters (e.g., intercept, slope, quadratic term, volatility) as potential predictors of homeless nights. This invaluable information may be used to detect high-risk situations that may be targeted in future “smart interventions.” EMA data will also allow us to address other important exploratory questions like: 1) what psychosocial changes occur as an individual moves from homelessness into housing, and 2) what effect do events like exposure to discrimination, violence, or hospitalization have on homeless nights.

Mediation. The PROCESS macro for SPSS/SAS (described in Hayes, 2013;¹³² and available online¹³³) will be used to conduct exploratory mediation analyses to identify variables that mediate the relation between condition and homeless nights and re-arrest outcomes. This method uses an ordinary least squares path analytic framework to estimate direct and indirect effects in single and multiple mediation models with bootstrapped confidence intervals. The macro can also be used to evaluate moderated mediation models including those with dichotomous outcomes (e.g., arrest vs. no arrest).

Ethics:

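### The exploratory mediation models specify no baseline covariates, so a mediator that condition shifts can be credited with an effect that belongs to its baseline level

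*Combined protocol and SAP*

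**What the plan says.** Objective c makes mediation one of its hypotheses: "These key variables are also hypothesized to mediate the relation between treatment condition and number of homeless nights and re-arrest". The variables meant include in-person measures (substance use, social support, distress, quality of life) and daily phone measures (affect, stress, discrimination, substance use).

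The Mediation paragraph under Statistics plans "exploratory mediation analyses to identify variables that mediate the relation between condition and homeless nights and re-arrest outcomes". It uses the PROCESS macro: "This method uses an ordinary least squares path analytic framework to estimate direct and indirect effects in single and multiple mediation models". Inference on the indirect effects is by bootstrap interval. It adds that moderated mediation and dichotomous outcomes can be handled. It does not mention covariates, or the baseline level of the mediator.

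Other analyses do address covariates. Aim 1 has an optional list. For Aim 2, "Covariates for analyses will include baseline characteristics that are known predictors of each outcome". For the Aim 3 re-arrest regression, "Covariates may include treatment group, age, gender, race/ethnicity, education, type of crime, and other variables as appropriate". The same Aim 3 paragraph adds: "Change scores (e.g., change in social support from baseline to the 1-month follow-up visit) will also be examined as potential predictors". None of these statements is extended to mediation, and none of the lists names the baseline level of a mediator.

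**The concern.** An indirect effect is the product of two paths: a, from condition to mediator, and b, from mediator to outcome given condition. The Study Design section says "This study is a 3-arm randomized controlled trial", and that protects a. Nobody is randomized to a level of the mediator, so b is an observational association.

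Distress, social support, quality of life and substance use are likely to persist within a person, so a follow-up value partly repeats the baseline value. If the baseline value also predicts later homeless nights or re-arrest, a model with only condition, mediator and outcome attributes that association to b. Once a is not zero, the spurious b is multiplied into the indirect effect, and the bootstrap interval can exclude zero although changing the mediator would do nothing to the outcome. At stake is the choice of mechanism for future interventions to target.

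**Working it through.** The plan gives no sample size, power or effect size for mediation, so there is no figure of its own to reproduce.

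**Inputs from the plan.** The Aim 1 paragraph gives 144 per group and 30% dropout: 144 × 0.70 = 100.8, about 101 completers per arm. (462 / 3 = 154 would give 154 × 0.70 = 107.8; the runs completed at 107 per arm were similar.)

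**Assumed inputs.** r is the correlation between baseline and follow-up mediator, g the effect of the baseline mediator on the outcome in SD, and a the shift of the mediator by condition in SD. Intervals are taken as 95% percentile bootstrap, since the plan states no level. The true effect of the follow-up mediator on the outcome is set to zero, so every interval that excludes zero is a false finding.

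**Formula check** (standardized variables, n per arm, no baseline adjustment):

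- Spurious b = r × g. Spurious indirect effect = a × r × g.
- z for a = a / √(2/n).
- z for b = rg / √((1 − r²g²)/(2n − 3)).
- False mediation rate ≈ P(a significant) × P(b significant).

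With r = 0.6, g = 0.4, a = 0.3, n = 101:

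- Spurious b = 0.24; spurious indirect effect = 0.3 × 0.24 = 0.072.
- z for a = 0.3 / 0.1407 = 2.13, probability about 0.57.
- z for b = 0.24 / √(0.9424/199) = 0.24 / 0.0688 = 3.49, probability about 0.94.
- Product: 0.57 × 0.94 ≈ 0.53. Simulation gave 52%.

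**Simulated share of intervals excluding zero, continuous outcome, 100 or 101 per arm:**

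| r | g | a | Unadjusted | Baseline mediator in both equations |
|---|---|---|---|---|
| 0.5 | 0.3 | 0 | 3.0% | 0.2% |
| 0.6 | 0.5 | 0 | 6.4% | 0.2% |
| 0.5 | 0.2 | 0.2 | 8% | 5% or less |
| 0.5 | 0.3 | 0.2 | 13.4% | 0.4% |
| 0.6 | 0.2 | 0.3 | 17% | 3.5% |
| 0.5 | 0.3 | 0.3 | 26.8% | 2.2% |
| 0.6 | 0.5 | 0.2 | 30.6% | 2.0% |
| 0.6 | 0.4 | 0.3 | 52% | 4% |
| 0.6 | 0.5 | 0.3 | 53.8% | 3.0% |
| 0.6 | 0.4 | 0.4 | 73% | 5% |

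The most extreme corner of the assumed ranges (r 0.6, g 0.5, a 0.4) is not in the table. The formula puts it slightly higher: z for a = 0.4 / 0.1407 = 2.84 (probability 0.81), z for b = 0.30 / √(0.91/199) = 4.44 (probability 0.99), product about 0.80. The largest adjusted rate in any of the tabulated or related runs was 6.6%, at a shift of 0.5 SD. Monte Carlo error is about 1 point near 5% and 2 to 3 points near 50%.

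**Binary outcome** (logistic outcome model, about 50% re-arrested, in line with the Background's statement that more than half of adults released from Texas county jails are re-arrested within a year; 100 per arm, r 0.6, a 0.3): with a baseline odds ratio of 1.5 per SD, 19% unadjusted against 4% adjusted; with 2.0, 40% against 3%.

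**Power when the mediator truly acts** (0.25 SD): 55% to 59% unadjusted, 60% to 62% adjusted. Adjustment does not cost power here.

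**The case against.** The strongest reply is that the paragraph is silent, not committed to unadjusted models. A reader might infer that the sponsor has chosen to adjust for nothing. The documents do not support that. The Aim 3 paragraphs on mixed models for homeless nights also list no covariates, so silence is partly drafting style, and the re-arrest regression in the same aim leaves room for further variables. This stands: the defect is that the adjustment is unspecified. But carrying those lists over would not cure it, because none names the mediator's own baseline level.

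A reader might also infer that any mediator whose baseline tracks the outcome will be reported as carrying the treatment effect. That does not follow. Condition is independent of the baseline mediator by randomization, so when condition leaves the mediator unmoved the indirect effect centres on zero however confounded b is. The no-shift rates of 3.0% to 6.4% show this. At a shift of 0.1 SD the rate is still only 2.5% to 10%.

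The sizes rest on assumed r, g and a, and on how residual variance is set. With unit-variance errors instead of standardized variables, the rates at a shift of 0.3 SD fall to 9% to 34%. Homeless nights, a bounded count, was not simulated as such.

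Finally, the analyses are labelled exploratory. That limits the consequence, but it does not remove confounding from an estimate, and objective c still states mediation as a hypothesis.

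**Conclusion.** The concern holds as a specification gap with a real bias behind it. Run with only the terms it names, the mediation model leaves the non-randomized path open to confounding by the mediator's baseline level. The bias needs a shift in the mediator, which is what the plan expects: Aim 2 assumes a 24% greater decrease in psychiatric symptoms and 30% fewer alcohol and drug use days in SPCM than in UCM. The documents give no SDs, so those percentages cannot be turned into the shift used above.

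Under the assumed ranges, false mediation is roughly 8% to 73% across the combinations simulated, about 80% by formula at the extreme corner, and about 5% or less with baseline adjustment. With no shift it is near 5% either way or lower. Baseline adjustment removes this source of confounding only; other common causes of mediator and outcome remain. Because the analyses are exploratory, this is something the plan should correct. It does not threaten the primary comparisons.

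**What to change.** Add to the Mediation paragraph: each PROCESS model for homeless nights and re-arrest includes, in both the mediator and the outcome equation, the pre-randomization value of every in-person mediator in that model, together with the Aim 2 baseline covariates (age, race/ethnicity, employment status, criminal history, lifetime homelessness).

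In-person questionnaires are given at baseline, so no new data should be needed. The schedule of individual measures is in an appendix not available here, and some measures are completed at the randomization visit. The sponsor should confirm that each mediator has a value taken before allocation.

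Mediators measured only by daily phone assessment need their own sentence. Those assessments start the day after the randomization visit and only in the two smartphone arms, so they have no pre-randomization value and do not exist in UCM. Limit these models to UCM+SP versus SPCM, and use the closest baseline questionnaire in Table 2 (for example affect, perceived stress or discrimination) as a proxy covariate, described as such.

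The cost is a few sentences and a few degrees of freedom per model. Fixing the covariates in advance also removes a choice that would otherwise be made after seeing the data.
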